## **Statistical Analysis Plan**

Mean and standard deviation were calculated for each parameter. The normal distribution was analyzed using the Shapiro-Wilk test. Demographic data were analyzed using the t-test for independent variables. The differences between the full-mouth variables were analyzed using a Generalized Estimated Equations Model and the reductions were evaluated by Generalized Linear Models, adjusted to baseline when indicated. The post-hoc test applied for each peer comparison was Bonferroni. The data were analyzed using the concepts of per-protocol and intention-to-treat. The statistical analysis was performed using significance level of 5%, using IBM SPSS.

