## Study Protocol

This double-blind, placebo-controlled, randomized clinical trial was designed to evaluate the superiority of PUFA ω-3 + ASA vs. control. The study followed the CONSORT 2010 and the SPIRIT 2013 Statements. The trial was approved by the human subjects ethics board of Unesp (CAAE 66096817.3.0000.0077) and was conducted under the principles of the Helsinki Declaration of 1975, as revised in 2013. The study protocol was registered in ClinicalTrials.gov (NCT03093246).

Subjects with generalized grade C periodontitis were selected at the Division of Periodontics, Institute of Science and Technology, São Paulo State University (Unesp), Brazil. A complete dental exam was carried out and medical records were obtained. Subjects who fulfilled the inclusion criteria were invited to participate in the study. Each subject provided informed consent after a thorough explanation of the nature, risks, and benefits of the clinical investigations. The inclusion criteria were: 1) diagnosis of stages III/IV generalized grade C periodontitis (Papapanou et al, 2018); 2) presence of  $\geq 20$  teeth, excluding third molars and teeth indicated for extraction; 3) presence of  $\geq 6$  sites presenting PD  $\geq 5$  mm with bleeding on probing (BoP) and  $\geq 2$  sites with PD  $\geq 7$  mm (including incisors and first molars, in addition to three other non-contiguous teeth between them); 4) good general health; 5) at least 18 years old; and 6) agree to participate in the study and sign a written consent. Patients who 1) were pregnant or nursing; 2) were suffering from any other systemic disease (e.g., cardiovascular, diabetes, blood dyscrasias, immunodeficiency, etc.); 3) received antimicrobials or anti-inflammatory drugs in the previous 6 months; 4) received a course of periodontal treatment within the last 12 months; 5) smoked  $\geq 10$  cigarettes/day; 6) reported an allergy to ASA or seafood; 7) required antibiotic prophylaxis; 8) were currently using medication that could interfere with periodontal response; or 9) reported gastritis and/or gastric ulcers were excluded.

The randomization was done as follows: a researcher ([name]) generated a random computer sequence to determine the order in which the treatments would occur (test/control) according to the established sample. This sequence was kept in a brown/opaque envelope and was followed as the subgingival debridement were performed . The treatment was revealed only after the

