debridement session, when the patient received the pills. The professional responsible for patient recruitment ([name]), treatment ([name]), and the clinical measures ([name]) were distinct.

The sample size of the study was calculated based on the results obtained by a previous study that evaluated the effect of daily supplementation of  $\Omega$ -3 PUFA and low-dose ASA in the treatment of chronic periodontitis (El-Sharkawy et al., 2010). Considering  $\alpha = 5\%$  and  $\beta = 20\%$  (80% power) to detect an intergroup difference of at least 1.2 mm in the PD of pockets  $> 5$  mm, with a standard deviation of 0.8 mm, 16 patients would be needed in each group. To compensate possible attritions, 19 patients per group were included, obtaining a power  $> 80\%$ .

All diseased sites were instrumented in a single session by a trained operator ([name]). The patients received local anesthesia and one-stage full-mouth ultrasonic debridement (FMUD) (Wennström et al., 2005) by an ultrasonic device with specific tips for subgingival scaling. The patients were assigned to the following groups according to the randomization:

- Test Group (TG) (n=19): FMUD associated with 900 mg PUFA  $\Omega$ -3 + 100 mg ASA daily for 180 days;
- Control Group (CG) (n=19): FMUD and placebo.

All clinical measures were performed by one calibrated and blinded researcher ([name]). Clinical measures were performed at baseline, 3 and 6 months after the treatment, in all teeth, except third molars. The following clinical parameters were evaluated: 1) Probing depth (PD): distance from the bottom of sulcus/pocket to gingival margin; 2) Clinical attachment level (CAL): distance from the bottom of sulcus/pocket to cement–enamel junction (CEJ); 3) gingival recession (GR): distance from gingival margin to CEJ; 4) full-mouth plaque index (FMPI); and 5) full-mouth bleeding on probing (BoP). The clinical measures were assessed using a manual probe (North Carolina, Hu-Friedy). In addition, PD, CAL and GR measurements were done at six sites per tooth (mesiobuccal, buccal, disto-buccal, distolingual, lingual, and mesiolingual).

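### The SAP gives two overlapping between-arm analyses of the full-mouth parameters, GEE on the variables and GLM on the reductions, and does not say which one decides superiority

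*Combined protocol and SAP*

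**What the plan says.** The trial has one stated aim. Under Study Protocol it is described as a "randomized clinical trial was designed to evaluate the superiority of PUFA ω-3 + ASA vs. control". The data come at three times: "Clinical measures were performed at baseline, 3 and 6 months after the treatment, in all teeth, except third molars".

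The Statistical Analysis Plan assigns two model families to these data: "The differences between the full-mouth variables were analyzed using a Generalized Estimated Equations Model and the reductions were evaluated by Generalized Linear Models". The same sentence makes baseline adjustment of the reductions conditional and gives no criterion. The next sentence applies Bonferroni to the post-hoc pairwise comparisons. The section closes with one error level: "The statistical analysis was performed using significance level of 5%, using IBM SPSS".

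The section does not say:
- which model decides superiority for a parameter, or what follows if the two disagree;
- which GEE term compares the arms (level at a visit, overall group effect, or group-by-time);
- whether Bonferroni extends across the GEE and GLM results.

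**The concern.** For one parameter at one follow-up visit, comparing arms on the level and comparing them on the reduction are two tests of the same treatment effect. With neither named as decisive, superiority could be read from whichever is significant. The stated 5% would then not be the error rate delivered for that parameter. When the true effect is moderate, the two tables could also leave the question open, with significance in one and not in the other. The open choice on baseline adjustment adds to this, because it decides how closely the GLM test overlaps the GEE test.

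**Working it through.** **Inputs from the documents.** 19 per arm; 5% level (sidedness not stated, two-sided taken); planned difference 1.2 mm and SD 0.8 mm, both from the sample-size paragraph under Study Protocol ("80% power) to detect an intergroup difference of at least 1.2 mm in the PD of pockets"; "with a standard deviation of 0.8 mm, 16 patients would be needed in each group").

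**Assumptions.** Correlation ρ between baseline and follow-up of 0.3-0.7; equal variances; normal outcomes. The 0.8 mm belongs to probing depth in deep pockets. Using it for a full-mouth parameter is an assumption, and it cannot describe plaque or bleeding scores.

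**Step 1. Overlap of the two tests.** Let Y0 be baseline and Y1 follow-up, each with variance σ².
- Level against unadjusted reduction: Cov(Y1, Y0 − Y1) = −(1 − ρ)σ² and Var(Y0 − Y1) = 2(1 − ρ)σ². The correlation in absolute value is √((1 − ρ)/2).
- Level against baseline-adjusted reduction: the adjusted quantity is Y1 − ρY0 apart from sign, with variance (1 − ρ²)σ² and covariance with Y1 of (1 − ρ²)σ². The correlation is √(1 − ρ²).

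**Step 2. Error with no true effect.** P(at least one significant) = 5% + 5% − P(both), from the bivariate normal distribution.

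| ρ | Correlation, unadjusted | Either significant | Correlation, adjusted | Either significant |
|---|---|---|---|---|
| 0.3 | 0.59 | 8.8% | 0.95 | 6.4% |
| 0.5 | 0.50 | 9.1% | 0.87 | 7.3% |
| 0.7 | 0.39 | 9.4% | 0.71 | 8.3% |

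Simulation with 19 per arm gives 8.9, 8.9 and 9.3% (unadjusted) and 6.3, 7.1 and 8.3% (adjusted). The plan's 5% is recovered when the tests coincide (adjusted case, ρ = 0, correlation 1). The ceiling for two independent tests is 1 − 0.95² = 9.75%.

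**Step 3. Other readings of the GEE test.**
- Group-by-time contrast at the visit with unadjusted reduction: the same contrast, so duplication adds nothing. Simulated error is about 6.4%, all of it from using an uncorrected robust Wald test with 19 per arm.
- Group-by-time with adjusted reduction: about 7.7-8.9%, part of which is the same Wald excess.
- Level test with Bonferroni over 3 pairs (arms at each visit): about 5.2-7.2%. With exact tests it could not exceed 5%/3 + 5% = 6.67%; anything above that is Wald excess. Over 15 pairs (all pairs of the 2 × 3 = 6 arm-by-visit cells): about 4.9-5.6%.
- Level test by uncorrected robust Wald: about 7.3-11.1%.

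**Step 4. How often one test is significant and the other is not** (level t-test against reduction, 19 per arm).

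| True difference | In SD units | Unadjusted reduction, ρ = 0.3 / 0.5 / 0.7 | Adjusted reduction, ρ = 0.3 / 0.5 / 0.7 |
|---|---|---|---|
| 0.6 mm | 0.6/0.8 = 0.75 | 31.7 / 32.5 / 34.5% | about 10 / 18 / 30% |
| 1.2 mm | 1.2/0.8 = 1.5 | 3.5 / 1.0 / 0.4% | 0.4 / 0.6 / 0.4% |

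With no true effect the figure is about 3-9% of all trials.

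**Step 5. Why one adjusted model is enough.** With Y0 as a covariate in both, regressing Y1 or Y0 − Y1 on arm gives the same arm effect apart from sign and the same p-value. The figures in steps 2 and 4 arise because at least one of the two tests is not baseline-adjusted.

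**The case against.** The strongest reply is that the inflation rests on a reading the plan does not state. The SAP does not say that significance in either model counts as success, that the GEE arm test is on level, or explicitly that the reductions are of the same full-mouth variables. It does mention Bonferroni. If that covers the GEE pairs, the excess is small; if the GEE test is group-by-time and the reduction unadjusted, the duplication is harmless. The correlation is assumed. Disagreement is common only when the true effect is well below the planned one. All of this stands, and it limits the size of the point.

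It does not remove the point. The plan does not commit to the one pairing in which the two tests coincide, and it attaches Bonferroni to post-hoc pairs rather than to the GEE and GLM results together. A reader cannot tell from the SAP which p-value answers the trial's question.

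A reader might infer that the trial's error rate simply is 6-9%, or that a false claim of benefit was made. The documents support neither. The first needs the either-counts rule, which is absent, and the Abstract reports no difference between treatments in the clinical parameters. The weakness is in the plan, not in a shown result.

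A fair reply to the remedy is that a model with one p-value at each follow-up visit still gives two chances per parameter. The baseline-adjusted tests at 3 and 6 months have correlation ρ/(1 + ρ) = 0.23-0.41 if all three visits are equally correlated, and an either-significant chance of about 9.3-9.6%. The fix must therefore name one visit.

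**Conclusion.** The point holds in a limited form: two overlapping between-arm analyses and no decisive one. The error is about 6-9% per parameter, visit and analysis set, conditional on a level-type GEE test without Bonferroni, an either-counts reading and ρ of 0.3-0.7. Across the other readings it runs from about 5% to 11%, and the top of that range reflects the uncorrected Wald test as well as duplication.

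It would be tempting to say that the two verdicts often disagree. That is true at a moderate difference such as 0.6 mm (about 10-35% of trials), but not at the planned 1.2 mm (at most about 3.5%). A disagreement here means significant against not significant, not effects in opposite directions. The gap is worth correcting and does not by itself undermine the trial.

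**What to change.** Use one between-arm model per parameter: the 3- and 6-month values on arm, visit, arm-by-visit and the baseline value, always baseline-adjusted. Name one visit's arm difference in advance (for example 6 months, the end of the 180-day treatment) as the only decisive test for that parameter, reported with its 95% CI. Treat the other visit as secondary. Report mean reductions per arm descriptively, without a second between-arm p-value.

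This also settles when baseline adjustment applies. At a true difference of 0.75 SD, a baseline-adjusted test has simulated power of 64-87%, against 61% for the level test and 47-83% for the unadjusted reduction. It does not deal with multiplicity across the several parameters or the two analysis sets.

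The cost is SAP wording, with the same data and software and fewer tests. The small downside is that one set of p-values disappears from the tables.

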## **Abstract**

**Background:** Periodontal destruction results mainly from the exacerbated host inflammatory response to the bacterial challenge. For this reason, research involving the modulation of host response has been developed aiming to facilitate the resolution of inflammation, as well as to promote tissue repair and periodontal stability. Recently, the use of omega-3 polyunsaturated fatty acids ( $\Omega$ -3 PUFA) and low-dose acetylsalicylic acid (ASA) was related to the production of enhanced lipidic mediators and to better clinical outcomes in the treatment of chronic periodontitis.

**Objective:** The aim of the present randomized controlled clinical trial was to evaluate the use of 900 mg  $\Omega$ -3PUFA and 100 mg ASA for 180 days as adjuvants to the non-surgical treatment (NST) of generalized aggressive periodontitis (GAgP).

**Methods:** Thirty-eight GAgP patients were submitted to subgingival debridement associated with  $\Omega$ -3 PUFA and ASA (n=19) or placebo (n=19).

**Results:** Both groups showed a statistically significant decrease ( $p<0.05$ ) in all clinical parameters, as well as a decrease in IL-1 $\beta$ , with no difference between treatments ( $p>0.05$ ). The TIMP-2 level significantly decreased in the control group and remained stable in the test group.

**Conclusion:** The proposed new therapy did not bring clinical benefits in the non-surgical treatment (NST) of GAgP.

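### Reductions are adjusted for baseline only at an unstated discretion; always adjusting costs 3 to 4% in variance at worst and gains precision unless the follow-up-on-baseline slope is near 1

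*Combined protocol and SAP*

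**What the plan says.** The Statistical Analysis Plan is one paragraph. For the changes from baseline it states that "the reductions were evaluated by Generalized Linear Models, adjusted to baseline when indicated". Neither that paragraph nor any other part of the document says what makes adjustment indicated, for which parameters or visits, or who decides and when.

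The Study Protocol section states: "Clinical measures were performed at baseline, 3 and 6 months after the treatment". Each clinical parameter (PD, CAL, GR, plaque index and BoP) therefore has a baseline value.

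The same SAP sentence begins: "The differences between the full-mouth variables were analyzed using a Generalized Estimated Equations Model". It does not say whether baseline enters that model as a covariate or as one of the repeated outcomes. The analysis sets are covered by "The data were analyzed using the concepts of per-protocol and intention-to-treat", with nothing on whether the adjustment is the same in both.

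**The concern.** With an undefined trigger, two analysts could follow this plan and report different between-arm estimates for the same reduction, one adjusted and one not. Three things are at stake.

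- **Precision.** A reduction subtracts the whole baseline value, which is optimal only when the regression slope of follow-up on baseline is 1. Otherwise the unadjusted comparison carries avoidable noise.
- **Centring.** With 19 per arm, chance baseline differences are to be expected. Below a slope of 1, the unadjusted comparison then favours the arm that started deeper; above 1, the arm that started shallower.
- **Discretion.** The wording does not exclude deciding on adjustment after the results are seen.

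Interval width and centring matter here because the Abstract reports the comparison of clinical parameters and IL-1β as "with no difference between treatments". After a null result, a reader needs the interval to judge which effects remain plausible.

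**Working it through.** **Inputs from the document.** 19 per arm; planned difference 1.2 mm and SD 0.8 mm (sample-size paragraph of the Study Protocol); significance level 5%, taken as two-sided.

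**Assumptions not in the document.** Baseline-to-follow-up correlation ρ of 0.3, 0.5, 0.7 or 0.9; ratio k = baseline SD / follow-up SD; normally distributed patient-level values; all 38 patients analysed; 0.8 mm is the follow-up SD (the text does not say whether it is a single-visit SD or the SD of change). Results apply to the mm measures; plaque index and BoP may behave differently.

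**The plan's own figure.** The plan gives no figure for this point. Its sample size of 16 per group does not follow from its stated inputs: 2 × (1.96 + 0.84)² × (0.8/1.2)² ≈ 7 per group, or 9 by exact t. That is a separate matter. On those inputs, 19 per group has 99.4% power.

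**Variance of the between-arm contrast**, in units of the follow-up variance:
- unadjusted reduction: 1 + k² - 2ρk, which is 2(1 - ρ) when k = 1
- baseline-adjusted: (1 - ρ²) × (1 + 1/(2n - 4)); at n = 19 the last factor is 1 + 1/34 = 1.029
- slope of follow-up on baseline: ρ/k

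Example, k = 1 and ρ = 0.5: 0.75 × 1.029 / 1.00 = 0.77.

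| Adjusted / unadjusted variance | ρ 0.3 | 0.5 | 0.7 | 0.9 |
|---|---|---|---|---|
| k = 0.6 | 0.94 | 1.02 | 1.01 | 0.70 |
| k = 0.8 | 0.81 | 0.92 | 1.01 | 0.98 |
| k = 1 | 0.67 | 0.77 | 0.88 | 0.98 |
| k = 1.25 | 0.52 | 0.59 | 0.65 | 0.63 |

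The maximum is 1.03, at slope 1. With 16 per arm the factor is 1 + 1/28, so the worst loss is about 3.6%. With equal SDs, adjustment loses only above ρ ≈ 2/1.029 - 1 = 0.94. Simulation (40,000 to 60,000 trials per cell) gave the k = 1 ratios to within about 0.01.

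**Interval half-width**, k = 1: t × 0.8 × √(2/19 × variance above), with t on 36 df (unadjusted) or 35 df (adjusted). At ρ = 0.3 this is 0.62 mm unadjusted and 0.51 mm adjusted; at ρ = 0.7, 0.41 and 0.38 mm.

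**Shift from chance imbalance.** Reduction = baseline - follow-up, so a baseline difference d moves the unadjusted contrast by d - slope × d = (1 - slope) × d. One standard error of d is 0.8 × √(2/19) = 0.26 mm; at slope 0.5 the shift is 0.13 mm.

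**Type I error by rule** (simulated, k = 1, ρ = 0.3/0.5/0.7/0.9):
- Unadjusted, fixed in advance: about 5% overall. This averages about 10/9/7/6% when the baseline imbalance exceeds 1 SE and 2.5/3.2/3.9/4.6% when it does not.
- Always adjusted: about 5%.
- Adjusted only if the baseline difference has p < 0.05: about 4 to 5%. Mean interval width is 0.995 to 1.003 of the unadjusted width. Estimator variance falls by about 8/6/3/0.5%, against 33/22/13/2% if always adjusted.
- Smaller of the two p-values: 7.8/7.3/6.7/6.2%.

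**Power at 1.2 mm.** With k = 1 and ρ = 0.3, 96.7% unadjusted against 99.6% adjusted, a gain of about 3 points; less at higher ρ. With k = 1.25 and ρ = 0.3 it is 91.6% against 99.6% (8 points). With k = 1.67 and ρ = 0.3 it is 76.9% against 99.6% (about 23 points).

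**The case against.** The strongest reply is that an unadjusted comparison of reductions is a legitimate randomised analysis and that the gain rests on a correlation and an SD ratio the document does not give. The powered outcome is PD in pockets deeper than 5 mm. If those pockets are picked on baseline depth, the baseline spread may be compressed (an inference), which puts k below 1, where several cells above show little or no gain. The trial is also already analysed, so always-adjusted estimates can only be post hoc. All of this stands, and it limits how large a gain can be claimed. It does not supply the missing criterion, and it does not alter the asymmetry between a loss of 3 to 4% at worst and a gain that may be substantial.

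A reader might infer more than the document supports:
- *That the unadjusted analysis is invalid or biased.* It is not, if fixed in advance; its overall type I error is about 5%.
- *That the investigators chose the more favourable result.* The wording leaves room for it, but nothing shows it happened.
- *That the null finding is an artefact.* The document does not say whether the GEE or the GLM produced it, nor which reductions were adjusted.
- *That the GEE ignored baseline.* No section says so. The within-group decreases in the Abstract and the Bonferroni pairwise tests suggest, without stating it, that baseline was a repeated time point.

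**Conclusion.** The concern holds in limited form. The criterion for adjustment is missing, although adjustment was always possible. Among the fixed-in-advance options, always adjusting is the better rule: the variance saving is about 33/22/13/2% under equal SDs and ρ of 0.3/0.5/0.7/0.9, larger if the baseline SD exceeds the follow-up SD, and absent when the slope is near 1. Reading the wording as a test of baseline imbalance recovers little of this.

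The bound on the loss is firm for the model assumed; the size of the gain depends on the assumed ρ and k. Power at the planned difference is a weak argument under equal SDs and a stronger one only if baseline values are the more variable. The case for change is a tighter and better-centred interval and one fewer open choice. It is worth fixing, but it does not invalidate the trial. How baseline enters the GEE is a reporting clarification only.

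**What to change.** State that every GLM of a reduction includes the baseline value of the same parameter, whatever the observed imbalance, at each visit and in both the per-protocol and intention-to-treat analyses. Report the adjusted between-arm difference with its 95% CI.

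Because results are known, disclose which reductions were originally adjusted and by what criterion. Present the always-adjusted estimates as a labelled post hoc analysis beside the original, not in its place. Add one sentence saying whether baseline is a covariate or an outcome time point in the GEE.

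Cost: a few sentences, one degree of freedom per model (residual 36 to 35 with all 38 patients), 3 to 4% in variance at worst, and a rerun on existing data.

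### The reductions are tested by generalized linear models in at most 38 patients with no stated reference distribution; a large-sample Wald test would run at about 5.8% to 6.8% rather than 5%, and a linear model with a t or F reference would settle it.

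*Combined protocol and SAP*

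**What the plan says.** The Statistical Analysis Plan gives the reductions one clause: "the reductions were evaluated by Generalized Linear Models, adjusted to baseline when indicated". The level and software follow: "The statistical analysis was performed using significance level of 5%, using IBM SPSS". It also states that "The data were analyzed using the concepts of per-protocol and intention-to-treat", so some analyses may include fewer patients than were randomized.

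On numbers, the Abstract reports that "Thirty-eight GAgP patients were submitted to subgingival debridement". The Study Protocol section explains the total: "16 patients would be needed in each group", and "To compensate possible attritions, 19 patients per group were included". Clinical measurements were taken at baseline, 3 months and 6 months.

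The plan does not state:
- the error distribution, link or scale estimator of the generalized linear model;
- whether treatment is tested by Wald, likelihood-ratio, t or F;
- any small-sample correction;
- when baseline adjustment counts as indicated;
- whether the test is one- or two-sided;
- what follows if the normality check fails.

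**The concern.** Each reduction gives one value per patient per visit. For a continuous outcome of that kind, a linear model with a t or F reference holds its level exactly under normal errors, however small the sample. A generalized linear model covers that case, but it is a wider class. Tests within it may instead refer to the normal or chi-square distribution, which ignores the uncertainty in the estimated residual variance. With 19 patients per arm that uncertainty is not negligible, and such a test rejects a true null hypothesis more often than its nominal rate.

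The name of the model therefore does not settle whether the 5% level is held. The open rule on baseline adjustment adds to the gap, because the size of the excess depends partly on whether the covariate is in the model.

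**Working it through.** **Inputs from the documents.** The nominal level is 5%. There are 38 patients, 19 per arm. The calculated requirement of 16 per arm (32 in total) serves here as a smaller analysis size.

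**Inputs that are assumed.** The test is two-sided, with normal errors and identity link. The documents give no number of completers, so 32 is a scenario.

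**The plan's own figures.** On this point the plan's only figure is the nominal 5%. The 16 per group is used below only as a scenario, and it does not follow from its stated inputs ("80% power) to detect an intergroup difference of at least 1.2 mm", "with a standard deviation of 0.8 mm"). The normal approximation gives 2 × (1.960 + 0.842)² × (0.8/1.2)² = 6.98, so 7 per group, and the t-based calculation gives 9. That is a separate matter and does not enter the calculation of the level.

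**Step 1: degrees of freedom.** With p mean parameters, df = N − p. Here p = 2 for treatment alone and p = 3 with the baseline covariate.

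**Step 2: Wald statistic against the t statistic.** Let t be the usual linear-model statistic, with scale SSE/df.
- Residual scale: the Wald statistic equals t but is compared with 1.960. Level = 2·P(t_df > 1.960).
- Maximum-likelihood scale (SSE/N): the Wald statistic equals t·√(N/df). Level = 2·P(t_df > 1.960·√(df/N)).

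**Step 3: numbers.**

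| N | Model | df | Exact t cut-off | Level, residual scale | 1.960·√(df/N) | Level, maximum-likelihood scale |
|---|---|---|---|---|---|---|
| 38 | treatment only | 36 | 2.028 | 5.8% | 1.908 | 6.4% |
| 38 | with baseline | 35 | 2.030 | 5.8% | 1.881 | 6.8% |
| 32 | treatment only | 30 | 2.042 | 5.9% | 1.898 | 6.7% |
| 32 | with baseline | 29 | 2.045 | 6.0% | 1.866 | 7.2% |

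**Step 4: other large-sample tests, N = 38.** A likelihood-ratio chi-square test has level 5.8% (treatment only) or 6.2% (with baseline). A Wald test with a sandwich variance was simulated with 100,000 trials per setting. It gave 6.5% to 6.9% with normal errors and 6.3% to 6.6% with skewed errors (gamma, shape 2).

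**Step 5: the alternative.** With a t or F reference the level is exactly 5% under normal errors. In the same simulations, at N = 38 and N = 32, it was 4.9% to 5.1% with normal errors and 4.7% to 4.9% with skewed errors.

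**Step 6: an interval, if one were reported.** The ratio of a maximum-likelihood Wald 95% interval to the exact t interval, adjusted for baseline, is 1.881/2.030 = 0.927 at N = 38 and 1.866/2.045 = 0.912 at N = 32. The interval would be 7% to 9% too narrow.

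**The case against.** The strongest objection is that no document mentions a Wald test. A normal, identity-link generalized linear model can be tested with t or F, and naming the software does not show which was used. Showing that both scale estimators exceed 5% does not answer this, because both calculations already assume the normal or chi-square reference. This objection stands. It limits the point to an unspecified reference distribution with a conditional consequence.

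The figures also rest on a normal model. Under another family neither the formulas nor the exactness of the t test would carry over. The 6.8% further assumes baseline adjustment, which the plan applies only in some cases. Both are fair, and for that reason the unadjusted figures and the skewed-error simulations are shown.

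A reader might infer three stronger things, none of which the documents support:
- **That the trial's tests exceeded 5%.** The test used is not stated, so this cannot be concluded.
- **That its confidence intervals are too narrow.** The documents neither plan nor report an interval. Step 6 only shows what a Wald interval would look like.
- **That the main conclusion is in doubt.** The Abstract reports no between-treatment difference in the clinical parameters or IL-1β. A test that rejects too often cannot explain a non-significant result. The Abstract's TIMP-2 statement describes change within each group and is not tied to any model, so nothing is rested on it.

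**Conclusion.** The point holds as a specification gap with a modest, conditional effect. With a large-sample Wald chi-square test, two-sided, normal errors and identity link, the actual level at nominal 5% is 5.8% to 6.8% with 38 patients, an excess of 0.8 to 1.8 percentage points. With an assumed 32 patients it is 5.9% to 7.2%, an excess of up to 2.2 points. With a t or F reference the level is 5%, and the only remaining change is to fix the baseline-adjustment rule.

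The change is worth making because it removes the doubt at almost no cost, but it is a minor improvement. It concerns the models for the reductions only. The estimating-equation analysis of the full-mouth variables was not examined here.

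**What to change.** For the continuous reductions at 3 months and at 6 months, replace the generalized linear model clause with wording such as: analysis of covariance (general linear model) at each visit, with treatment as factor and the baseline value of the same parameter always as covariate, tested two-sided with the t or F reference distribution, and the treatment difference reported with its 95% confidence interval.

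The outcome may be the reduction or the follow-up value. With baseline in the model, reduction = baseline − follow-up, so the treatment coefficient only changes sign and its standard error and test are identical. Always including baseline also removes the undefined condition for adjustment. Because exactness rests on normal errors, add a residual check, particularly for the plaque and bleeding indices.

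If a t or F reference was already used, it is enough to say so and to fix the baseline rule.

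**Cost.** One sentence in the plan and, since results are already reported, a small re-analysis that the same software can run. Where a large-sample reference was used, p-values become slightly larger: a maximum-likelihood Wald p-value of 0.05 with 38 patients and baseline in the model becomes 0.068. Adding baseline to a model that lacked it can move an estimate or p-value in either direction. The correction of the level alone is not expected to change the reported finding of no between-group clinical difference.
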